8.13 Safety Monitoring

A Data Safety Monitoring Board (DSMB) consisting of independent physicians and at least one independent statistician, who are not investigators in the study, nor have a conflict of interest with the conduct and administration of the study, will be convened on a regular basis to evaluate study progress and review adverse events.

An independent Clinical Events Committee (CEC) consisting of physicians, who are not investigators in the investigation, nor have a perceived conflict of interest with the conduct and administration of the investigation, will be established to adjudicate applicable clinical events reported during the investigation. This adjudication will be performed to assess whether the events were due to a pre-existing or unrelated condition, procedure-related, technique-related, and/or device-related.

A central core laboratory will be used for image analysis to provide uniformly defined morphological and morphometric analysis of images.

Regularly scheduled review/monitoring of all patient data will be conducted at the data coordinating center, in part, for identification of adverse events and assurance that they are correctly reported to the DSMB and CEC.

9.0 Statistical Considerations

9.1 Endpoint Analyses

For the primary effectiveness and safety endpoints, the hypotheses will be tested at the significance level of 0.025. If both the safety and effectiveness hypotheses are met, the study will be considered successful.

The test statistic for hypotheses testing of the secondary endpoint is the absolute change from baseline in the VCSS at 1 month and at 12 months. Paired t-test will be used to evaluate the secondary hypotheses. In the analyses of VCSS, multiplicity will be adjusted using the Holm procedure due to the presence of multiple time points.

Full statistical details (including endpoint analyses) are in the Statistical Analysis Plan for the study.

9.2 Sample Size Calculations

Evaluation of the primary safety hypothesis of 30-day freedom from MAE and the primary effectiveness hypothesis of 12-month primary quantitative patency requires 218 patients to determine if the performance goals have been met. Allowing for an additional 10% of patients who withdraw or are lost to follow-up, Cook intends to enroll 243 patients.

A Bayesian adaptive study was simulated to determine the sample size required to test the study hypotheses with sufficient statistical power (in the frequentist context). For the power calculations, the true quantitative patency rate following treatment with the Zilver® Vena™ Venous Stent was assumed to be 86% and the true rate of freedom from MAE at 30 days was assumed to be 97%. The results of the simulations indicate that a sample size of 218 will provide a minimum power of 0.90 with a Type I error of 0.025 for each endpoint.

It has been prespecified that patients enrolled in this study will include approximately 30% acute patients and 70% chronic patients. This patient population was defined based on the published literature describing patients treated for iliofemoral venous obstruction¹⁻³⁹ and the pattern of enrollment for the first 109 patients enrolled. Specific definitions for acute and chronic iliofemoral venous outflow obstruction are provided in Appendix B.

Full statistical details on sample size calculation are in the Statistical Analysis Plan for the study.

9.3 Site-level Poolability

Poolability of data from multiple sites will be verified by examining the primary safety and effectiveness measures among sites. Site-level poolability will be considered appropriate provided that these measures are similar among sites. It is expected that important patient baseline characteristics, such as age, sex/gender, BMI, lesion length, known thrombophilia, anticoagulation/antiplatelet medication usage, stent extension below the inguinal ligament, stent extension into the common femoral vein, stent expansion into the IVC, presence of occlusive obstruction, presence of reflux, adjunctive procedures performed in addition to stent placement (thrombolysis, thrombectomy, IVC filter), and previous DVT may differ among sites. The influence of these patient characteristics on site poolability will also be examined.

It is expected that some sites will have too few patients to provide reasonable site-level estimates of primary and secondary measures. Each investigative site will be allowed to enroll no more than 49 patients (20% of the total enrollment) to ensure the overall result is not biased by the results from a single site. Pooling of this information will be explored based on hospital size (large versus small), site enrollment (large versus small), type of hospital (community versus teaching), and other group-wise strategies.

US versus OUS poolability analysis will be accomplished by incorporating a covariate indicating whether a patient belongs to US or OUS.

9.4 Planned Subgroups, Interactions, and Covariates

In addition to the site level poolability, the primary and secondary endpoints will be analyzed against relevant demographic and comorbidity variables in the context of sub-group analyses or included in the analysis models as covariates.

The analysis may include the covariates of age, BMI, lesion length, known thrombophilia, anticoagulation/antiplatelet medication usage, sex/gender, stent extension below the inguinal ligament, stent extension into the common femoral vein, stent extension into the inferior vena cava, presence of occlusive obstruction, presence of reflux, adjunctive procedures performed in addition to stent placement (thrombolysis, thrombectomy, IVC filter), previous DVT, etc.

Planned subset analyses include: non-thrombotic versus post-thrombotic obstruction on chronic venous disease, occlusive versus non-occlusive obstruction, presence versus absence of

thrombophilia, stent extension into the IVC/common femoral vein, and presence versus absence of reflux.

9.5 Missing Data

Missing data will be addressed using two primary strategies: 1) multiple imputation with best available data, if appropriate, and 2) case deletion. The first strategy is multiple imputation with best available data, if appropriate. This method will be used to predict missing endpoint and imaging data. Previous clinical trial experience suggests that some portion of the imaging data may not meet the criteria for accurate review by the core laboratory; however, it is recognized that the investigator uses this information to provide the best possible care for the patient. Therefore, it is reasonable to substitute any missing core laboratory measurements with the corresponding measurements made by the investigator or institutional staff. In addition, the absence or presence of clinical sequelae may supplement the required missing core laboratory assessment of device performance. This strategy is a best approximation of the missing data value.

Statistical imputation strategies originating from Schafer⁴⁰ may also be used, supplemented with notes provided by Schafer.⁴¹ The computations (with no covariates) will be performed using PROC MI and PROC MIANALYZE in SAS version 9.3 or later, or WinBUGS 1.4 or later. Unless evidence suggests otherwise, missing at random data will be assumed.

The second strategy is case deletion. If the amount of missing data does not result in a reduction of analyzable patients to a number that is below that which is required for sufficient statistical power of the primary endpoints, then case deletion will be the method of choice for that analysis.

Additional analyses may also be performed to address missing data, including tipping point analysis.

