Occlusion, Early – No flow within the treated venous segment (including the region within ± 1 cm proximal and/or distal to the treated venous segment) occurring ≤ 24 hours of the procedure as demonstrated by duplex ultrasound or venography. An occlusion occurring within 24 hours of the procedure will be considered thrombotic in nature, regardless of whether it is successfully treated with thrombolysis/thrombectomy.

Occlusion, Intermediate – No flow within the treated venous segment (including the region within ± 1 cm proximal and/or distal to the treated venous segment) occurring > 24 hours after the procedure, but ≤ 30 days after the procedure as demonstrated by duplex ultrasound or venography. An occlusion occurring within 30 days of the procedure will be considered thrombotic in nature, regardless of whether it is successfully treated with thrombolysis/thrombectomy.

Occlusion, Late – No flow within the treated venous segment (including the region within ± 1 cm proximal and/or distal to the treated venous segment) occurring > 30 days after the procedure as demonstrated by duplex ultrasound or venography.

Outflow Obstruction – Documented iliofemoral venous obstruction (e.g., recanalization of the vein with multiple channels, documented collaterals as determined by imaging).

Patency, Clinical – Lack of occlusion of the treated venous segment determined by evidence of blood flow both proximal and distal to the study lesion assessed via ultrasound and/or venography and no worsening of pain or edema symptoms from baseline (according to Venous Clinical Severity Score; VCSS) as related to the target lesion.

Patency, Quantitative – A treated venous segment (including the region within ± 1 cm proximal and/or distal to the treated venous segment) minimum lumen diameter $> 50\%$ of the immediate post-procedure stented minimum lumen diameter as demonstrated by venography.

Patency, Primary Quantitative – A treated venous segment retains primary quantitative patency provided that uninterrupted (intervention-free) quantitative patency remains since the initial procedure as determined by the core laboratory. Failure of primary quantitative patency occurs at the time of one of the following: loss of quantitative patency, occlusion of the treated segment, surgical bypass of the treated segment, or amputation of the extremity determined to result from venous outflow occlusion.

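### Section 9.5 lets site measurements replace, and absence of clinical sequelae supplement, missing core-laboratory reads for a primary endpoint defined as core-laboratory determined

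*Combined protocol and SAP*

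**What the plan says.** Section 4.1.2 makes 12-month primary quantitative patency, assessed by venography, the primary effectiveness endpoint. Section 4.2.2 tests it against 76% with a one-sample binomial test at 0.025. Appendix B requires a minimum lumen diameter above 50% of the immediate post-procedure value and says the segment retains the endpoint if uninterrupted "quantitative patency remains since the initial procedure as determined by the core laboratory". It defines clinical patency (flow, and no worsening of pain or edema) as a separate outcome. Section 8.3 lists central core-laboratory image analysis among the measures against bias.

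Section 9.5 expects that "some portion of the imaging data may not meet the criteria for accurate review by the core laboratory". Its first strategy, multiple imputation with best available data, covers missing endpoint and imaging data. Under it, "it is reasonable to substitute any missing core laboratory measurements with the corresponding measurements made by the investigator or institutional staff". It adds that "the absence or presence of clinical sequelae may supplement the required missing core laboratory assessment of device performance".

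The second strategy is case deletion, preferred if the missing data "does not result in a reduction of analyzable patients to a number that is below that which is required for sufficient statistical power". Section 9.2 gives that number: the evaluation "requires 218 patients to determine if the performance goals have been met". Section 9.5 ends: "Additional analyses may also be performed to address missing data, including tipping point analysis".

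**The concern.** The first strategy weakens the endpoint in two ways.

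- **Reader.** An investigator who knows the device was implanted replaces an independent laboratory. With no control arm, nothing offsets a systematic difference between the two.
- **Evidence.** Absence of sequelae bears on clinical patency, which Appendix B keeps separate. It does not show that the lumen exceeds the 50% threshold. Presence of sequelae is less troublesome, because it may reflect occlusion, bypass or amputation, which Appendix B already counts as failure.

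Whenever the first strategy is in use, an asymptomatic restenosis with an unreadable venogram can therefore enter the primary analysis as patent.

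A secondary matter is that section 9.5 does not say whether a patient with only a site read or sequelae data is analyzable. The natural reading is that the count precedes substitution, but the text leaves this unstated.

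**Working it through.** **Inputs.** Goal 76% and level 0.025 (section 4.2.2); assumed true patency 86%, required number 218, enrolment 243 and 10% allowance (section 9.2). The unreadable-image rate and site-read accuracy are not given and are assumed below. The adaptive design mentioned in section 9.2 is not modelled; a fixed single-look exact binomial test stands in for it.

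**1. The plan's own figures.** 218/(1 − 0.10) = 242.2, rounded up to 243, as stated. The fixed exact test at 218 passes at 179, with size 0.0186 and power 0.956 at 86%, consistent with the stated minimum of 0.90. At 243 it passes at 198, with size 0.0247.

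**2. Effect of substituted reads at the null.** Let f be the share of reads substituted. Assume half of true failures are misread as patent and no patent segment is miscalled. The apparent rate is 0.76 + f × 0.24 × 0.5.

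| f | Apparent rate | False success, 243 analysed | False success, 218 analysed |
|---|---|---|---|
| 0 | 0.7600 | 0.025 | 0.019 |
| 1% | 0.7612 | 0.027 | 0.020 |
| 3% | 0.7636 | 0.033 | 0.025 |
| 5% | 0.7660 | 0.040 | 0.030 |
| 10% | 0.7720 | 0.062 | 0.047 |

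**3. The opposite direction.** If sites under-call (66% read as patent, 10% substituted), the apparent rate is 0.9 × 0.76 + 0.1 × 0.66 = 0.75, and false success falls to 0.010 (243) or 0.008 (218). The half-misread error is cancelled if sites miscall 0.24 × 0.5/0.76 = 15.8% of patent segments.

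**4. When substitution would be triggered.** The margin is 243 − 218 = 25 patients, and section 9.2 assigns it to withdrawal and loss: "Allowing for an additional 10% of patients who withdraw or are lost to follow-up". Counting before substitution, the first strategy is reached once 26 patients lack a core-laboratory result for any reason (243 − 26 = 217). With nobody lost, 10% unreadable leaves about 219 reads (243 × 0.90 = 218.7), so case deletion would still apply. The table thus shows what substitution does if used, not how often it will be used.

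**5. Power on core-laboratory reads alone.** At 86% true patency, fixed-design power is 0.956 with 218 reads, 0.948 with 196 and 0.916 with 185.

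**The case against.** The strongest reply is that the sections do not contradict each other: Appendix B defines the endpoint, and section 9.5 says what to do when its measurement is missing. Core-laboratory reads still govern every readable image. Substitution is confined to the corresponding measurement, and sequelae only supplement. Duplex ultrasound is also required at 12 months (section 8.7.6), so occlusion should be seen.

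Much of this stands: the rule is a fallback, permissively worded. But section 9.5 sets no limit on the weight of absent sequelae when the core-laboratory assessment is missing. The 12-month duplex is specified there for clinical patency, so it does not supply the venographic diameter.

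A reader might also infer that the unstated counting rule leads to conflicting verdicts or inflated error. The documents do not support that. Substitution sits inside the first strategy, so counting before it is the natural reading. With 25 patients lost and one image unreadable, the site read is usable under either count. With an assumed 10 lost and 12 unreadable, both counts (221 and 233) exceed 218. Passing if either count passes then gives false success of only 0.0240 with unbiased site reads. Nor is there a rate to show that the threshold is likely to be reached.

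Sections 9.1 and 9.2 defer full detail to a Statistical Analysis Plan that was not among the documents reviewed; it may settle some of this.

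**Conclusion.** The concern holds for the substitution and sequelae rule: when the first strategy is used, the primary endpoint can rest on evidence that Appendix B does not accept, and a silent restenosis can count as patent against a fixed goal. This should be changed. Confidence is medium, because the separate analysis plan was not available.

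The rise from 0.025 to 0.040 or 0.062 is an illustration under one-directional misreading with all 243 analysed. A reader might take it as the trial's actual error rate. The documents do not support that: they give no unreadable-image rate and no direction or size of site-read error, and at 218 analysed with 1% to 3% substituted the level stays at or below 0.025. The meaning of analyzable is a secondary clarification.

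**What to change.** In section 9.5:

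1. State that absence of clinical sequelae cannot establish quantitative patency.
2. Base the primary effectiveness analysis on core-laboratory determinations plus failures established under Appendix B (such as occlusion or bypass). Count analyzable patients on that basis, before any substitution. Keep the existing case-deletion rule.
3. Report site-read substitution as a sensitivity analysis, and change the tipping-point analysis from optional to committed.
4. If imputation is triggered, use site and duplex reads as predictors instead of substitutes, and amend the wording that excludes covariates.

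**Cost.** A few sentences, two sensitivity tables and slightly fewer analysed patients; fixed-design power stays above 0.90 even at 185 reads.

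There is also a bias to acknowledge. Keeping unread patients with known failures while deleting unread event-free patients pulls the estimate down. If 10% are unread and half of their failures are known, a true 76% becomes (0.9 × 0.76)/(0.9 + 0.1 × 0.24 × 0.5) = 0.684/0.912 = 75%. Conversely, deletion flatters the device if unreadable images are more often restenosed and those failures are not otherwise known. The tipping-point analysis should cover both directions.

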8.7.6 Follow-up Schedule

Follow-up windows are intended as guidelines only. They are not absolute and are not intended to limit data collection due to scheduling conflicts.

- *1-month clinic visit (30 days ± 5 days):* An office visit will be completed including documentation of VDS, CEAP “C” Classification, CIVIQ, and VCSS scores, and assessment of medications, hospitalizations and medical conditions.
- *3-month telephone contact (90 days ± 10 days):* Patients will be contacted by telephone by the investigative site for clinical evaluation and assessment of hospitalizations and medical conditions. Up to three attempts should be made to contact the patient.
- *6-month clinic visit (180 days ± 30 days):* An office visit will be completed including documentation of VDS, CEAP “C” Classification, CIVIQ, and VCSS scores, and assessment of medications, hospitalizations and medical conditions. Duplex ultrasound of the treated venous segment (including the cranial and caudal vessel segments) to assess clinical patency and 2 view stent x-ray (both obliques of the pelvis recommended) to assess device integrity will be performed. Confirmatory venography in approximately two orthogonal views will be performed if the patient is symptomatic and the ultrasound is inadequate to assess clinical patency.
- *12-month clinic visit (365 days ± 45 days):* An office visit will be completed including documentation of VDS, CEAP “C” Classification, CIVIQ, and VCSS scores, and assessment of medications, hospitalizations and medical conditions. Venography in approximately two orthogonal views will be performed of the treated segment and at least 1 cm cranial and caudal to the treated segment to assess quantitative patency. A calibration source (e.g., LeMaitre Ruler) will be in the field of view, but not overlapping the vessel. Duplex ultrasound of the treated venous segment (including the cranial and

caudal vessel segments) to assess clinical patency, and 2 view stent x-ray (both obliques of the pelvis recommended) to assess device integrity will be performed.

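### Section 9.5 assumes missing at random but specifies imputation without covariates; if 12-month patency is imputed on its own, that step only returns the complete-case result

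*Combined protocol and SAP*

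**What the plan says.** Section 9.5 (Missing Data) sets out two strategies.

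The first is imputation with best available data. On its scope the plan says: "This method will be used to predict missing endpoint and imaging data". Two substitutions come before any statistical model: "it is reasonable to substitute any missing core laboratory measurements with the corresponding measurements made by the investigator or institutional staff", and "the absence or presence of clinical sequelae may supplement the required missing core laboratory assessment of device performance". Statistical methods follow as an option; they "may also be used, supplemented with notes provided by" the author of the cited imputation text. The specification is then: "The computations (with no covariates) will be performed using PROC MI and PROC MIANALYZE in SAS version 9.3 or later", with WinBUGS as the alternative. The next sentence reads: "Unless evidence suggests otherwise, missing at random data will be assumed". Section 9.5 does not list the variables that enter the imputation.

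The second strategy is case deletion. If enough analyzable patients remain for power, "then case deletion will be the method of choice for that analysis". Tipping point analysis is mentioned as optional.

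Elsewhere, section 4.2.2 tests 12-month primary quantitative patency against 76% with a binomial test at 0.025. Section 9.2 requires 218 patients and enrolls 243 to allow for 10% withdrawal or loss to follow-up. Section 9.4 lists covariates that may be used in the endpoint analyses, among them occlusive obstruction, thrombophilia and lesion length. Section 8.7.6 schedules duplex ultrasound and VCSS at 6 months, with venography at that visit only in some patients: "Confirmatory venography in approximately two orthogonal views will be performed if the patient is symptomatic and the ultrasound is inadequate to assess clinical patency".

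**The concern.** Missing at random allows the chance of a missing result to depend on what has been observed about the patient. An imputation uses that assumption only if the observed predictors are in the model. With the 12-month status alone in the model, each missing value is drawn from the overall rate among patients who had a venogram. That is correct only if those patients are a random subset, which is missing completely at random. So the stated assumption and the stated computation do not match.

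The endpoint needs an invasive examination at 12 months. Patients who do not have it may differ from those who do, for example in their 6-month duplex result or symptoms. If they do worse, the rate from the remaining patients is too high. This is a single-arm comparison with a fixed goal, so there is no control arm in which the same bias could cancel. The trial already records variables that could reduce the bias, but the specification leaves them out.

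**Working it through.** **1. The plan's own figure, and when imputation comes into play.** 218/(1 − 0.10) = 242.2, rounded up to 243, as in section 9.2. Then 243 − 218 = 25. If 218 is the number required for power, case deletion is preferred with up to about 25 missing results, and statistical imputation matters beyond that.

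**2. What imputation without covariates returns.** Let N patients be enrolled, n observed, m = N − n missing, s patent among the observed, and p = s/n.

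- Expected pooled rate: [s + m(s/n)]/N = (s/n)(n + m)/N = s/n, the complete-case rate.
- Pooled variance with many imputations: within p(1 − p)/N, plus between p(1 − p)[m/N² + m²/(nN²)]. The sum is [p(1 − p)/N][1 + (m/N)(1 + m/n)]. Since 1 + m/n = N/n, this is [p(1 − p)/N](1 + m/n) = p(1 − p)/n, the complete-case variance.

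Numerical check (N = 243, beta posterior draws, 20,000 imputations):

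| Missing | Complete case (SE) | Imputed, no covariates (SE) |
|---|---|---|
| 25 | 179/218 = 82.11% (2.60) | 82.10% (2.60) |
| 36 | 170/207 = 82.13% (2.66) | 82.12% (2.66) |
| 49 | 159/194 = 81.96% (2.76) | 81.95% (2.76) |

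**3. How large the bias could be.** The documents give no missingness pattern and no patency by risk group, so all inputs here are assumed. Take a fraction q at higher risk, with patency p_a and missing fraction m_a, and the rest with p_n and m_n:

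observed rate = [q(1 − m_a)p_a + (1 − q)(1 − m_n)p_n] / [q(1 − m_a) + (1 − q)(1 − m_n)].

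True patency is set at 76% throughout.

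*Set A:* N = 243, q = 0.30, missingness depending only on the risk group; 3,000 simulated trials per row. The last three columns are mean estimates.

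| Patency, higher risk / rest | Missing, higher risk / rest | Missing overall | Expected bias (points) | Complete case | Imputed, no covariates | Imputed, risk group in model |
|---|---|---|---|---|---|---|
| 70 / 78.6% | 20 / 6% | 10.2% | +0.3 | 76.2% | 76.2% | 75.9% |
| 66 / 80.3% | 25 / 10% | 14.5% | +0.5 | 76.4% | 76.4% | 75.9% |
| 60 / 82.9% | 30 / 5% | 12.5% | +1.4 | 77.4% | 77.4% | 76.0% |
| 60 / 82.9% | 40 / 5% | 15.5% | +2.0 | 78.1% | 78.0% | 76.0% |

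The imputation without covariates keeps the bias. The imputation with the risk group removes it. The last three rows have more than 25 missing (0.145 × 243 = 35, 0.125 × 243 = 30, 0.155 × 243 = 38), which is where the step would be used under the 218 threshold.

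Rejection rates at a true 76% ran from 2.4% to 8.1% for the complete-case exact test, 4.1% to 12.3% for imputation without covariates, and 3.1% to 3.5% with the risk group. The imputation figures use a pooled Wald test, which adds some inflation of its own.

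*Set B:* q = 0.15, 10% missing overall. Worked row with p_a = 0.30 and m_a = 0.30: p_n = (0.76 − 0.045)/0.85 = 0.841; m_n = (0.10 − 0.045)/0.85 = 0.065; observed = (0.15 × 0.70 × 0.30 + 0.85 × 0.935 × 0.841)/0.90 = 0.778.

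| p_a | m_a | Observed rate | Bias (points) |
|---|---|---|---|
| 60% | 20% | 76.3% | +0.3 |
| 50% | 20% | 76.5% | +0.5 |
| 50% | 30% | 77.0% | +1.0 |
| 30% | 30% | 77.8% | +1.8 |
| 20% | 30% | 78.2% | +2.2 |
| 30% | 40% | 78.7% | +2.7 |

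If m_a = m_n, the observed rate is 76% and there is no bias.

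**The case against.** Much can be said for the plan, and several points stand.

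- *The step is optional and not the main tool.* Site readings and clinical sequelae come first, and both use information on the individual patient. Case deletion is preferred while power holds. A reader might infer that the plan as a whole can do nothing about missing-data bias; the text does not support that. The weakness lies in one optional step. Still, a site reading helps only if a venogram exists, and clinical sequelae enter without a stated rule.
- *With 10% missing, the step would not be used.* About 218 patients would remain, and case deletion would be chosen. For the last three rows of set B, the exact test at 218 (at least 179 patent) passes with probability 0.071, 0.092 and 0.125, against 0.019 at an unbiased 76%. A reader might take these as the cost of leaving out covariates. They are complete-case figures under strong assumed inputs, and changing the imputation model would not alter them. The milder rows of set B give 0.024 to 0.041. It remains true that case deletion makes the same assumption for the marginal rate.
- *A model without covariates need not contain only one variable.* The strategy covers endpoint and imaging data, so earlier imaging could be imputed jointly with the endpoint, which would give missing at random some content. The single-variable reading is the natural one but not certain. One should not say flatly that the plan assumes missing completely at random.
- *Many poor outcomes are not missing.* By the Appendix B definition, occlusion and loss of intervention-free patency count as failures, and section 8.7.8 requires venography at reintervention. This limits the bias but does not remove it for patients who are worse without having had such an event.
- *The detail may be elsewhere.* Sections 9.1 and 9.2 refer to a SAP for full statistical details, and no separate SAP text is in the combined document. Section 9.5 nevertheless makes a positive specification, which would need correcting wherever the detail sits.

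**Conclusion.** The point holds for the statistical imputation step. Section 9.5 pairs a missing-at-random assumption with a computation that, for 12-month patency imputed alone, has nothing observed to condition on. It then gives the complete-case rate and standard error and corrects no bias. The step matters most above about 25 missing of 243, provided 218 is the intended threshold.

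The algebra is exact under the single-variable reading. The size is not known: under the assumed inputs the upward bias runs from about +0.3 to +2.7 points against the 76% goal, and it is zero if missingness is unrelated to findings. The documents do not establish that the bias will occur, nor its direction. The mismatch should be corrected before the data are analyzed, because the correction is cheap and uses data already collected.

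**What to change.** In section 9.5 and the SAP:

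1. Delete the parenthesis that excludes covariates.
2. Impute the binary 12-month patency status with a logistic model (fully conditional specification in PROC MI), using a short prespecified list of predictors. Examples are acute or chronic disease, occlusive obstruction, 6-month duplex result, and VCSS pain and edema at the last visit. Include the 6-month duplex in the same chain, since it may itself be missing in patients lost early.
3. Keep the list short or penalize the model. At the planned 86% patency, 218 × 0.14 = 30.5, so about 30 failures are expected. Five predictors leave about six failures each; eight would leave about four, with a risk of separation.
4. State how the test against 76% is pooled across imputations. A plain pooled Wald test rejected in 3.1% to 3.5% of simulated trials even with the right predictor, so check the chosen rule against the 0.025 level.

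This edit does not change an analysis by case deletion. Reporting the covariate-based imputation beside it would cover the case of 25 or fewer missing.

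The cost is some programming and a modest burden of specifying the model in advance. No new data are needed.
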